9.3 Reporting of Serious Adverse Events by the Investigator

All SAEs must be reported by the investigator to the responsible Pharmacovigilance Safety Officer immediately without exceeding 24 hours after the SAE becomes known to the study team using the "Serious Adverse Event" form. The initial report must be as complete as possible, including details of the current illness and (serious) adverse event, information regarding onset, end date, severity, outcome and action taken with the IMP, an assessment of the causal relationship between the event and the trial medication.

All facts which require a benefit-risk reassessment of the study drug have to be reported promptly (that is within 15 days at latest) to IRB / EC. This includes particularly: expected SAE with unexpected outcome, increase in frequency of clinically relevant SAEs, unexpected SAE with assumed causal relationship after finalization of the investigator sponsored study and events which probably may harm the safety of the study patients. In the event of premature termination of the trial for safety reasons, the sponsor will inform the competent authority and IRB / EC without delay within a maximum period of 15 days.

EudraCT: 2021-001633-40	Version 1.7 15.01.2025	ESRA
-------------------------	---------------------------	------

If measures to protect study patients from immediate danger are taken IRB / EC have to be notified immediately.

At the time of the initial report, the investigator will fill in a SAE form comprising the following information:

- Patient/subject demographics
- Start and end date of treatment with the IMP
- Nature of the SAE including date of onset, severity and treatment (including hospitalization)
- Action taken with respect to the IMP
- Relationship to the IMP in the opinion of the investigator
- Relevant concomitant drug therapy, relevant medical history, relevant test and diagnostic procedures
- Outcome (clinical state at time of current observation)
- Recovery date (if available)
- In the case of death, the cause and post-mortem findings (if available).

9.4 Expedited Reporting

Unexpected SAE with assumed causal relationship (SUSARS) have to be promptly (that is within 15 days at latest; in case of SAEs, that lead to death or are life threatening: within 7 days and a follow up report within further 8 days) reported to all involved investigators and competent IRB / EC.

Investigators participating in this trial will report all SAEs to the responsible **Pharmacovigilance Safety Officer** by fax or e-mail using the **SAE form** as soon as possible but **not later than 24 hours** after their notification.

Additionally, all serious events as well as all other relevant safety information (e.g. pregnancy) have to be reported within one (1) working day following notice to
MSD SHARP & DOHME GmbH, department of Pharmacovigilance
[contact] or e-mail to [contact]

EudraCT: 2021-001633-40	Version 1.7 15.01.2025	ESRA
-------------------------	---------------------------	------

Any requested supporting documentation (e.g. ECG, laboratory results, autopsy report) should be sent to the same address stated above. This documentation may only be sent in pseudonymized form. The original SAE-reports and all other reports will be kept by the investigator.

Additionally, a list of all SAEs as well as a report about the safety of the study patients' needs to be submitted annually (or on demand) to the competent IRB / EC during the investigator sponsored study.

All initial reports and follow-up information (as many as required) will be pseudonymized and sent by fax or via e-mail.

At the time of the initial report, the investigator will fill in a SAE form comprising the following information:

- Patient/subject demographics
- Protocol number
- Start and end date of treatment with the IMP
- Nature of the SAE including date of onset, severity, chronicity and treatment (including hospitalization)
- Action taken with respect to test drug
- Relationship to test drug in the opinion of the investigator
- Concomitant drug therapy at the time of the adverse event
- Outcome (if available)
- Recovery date (if available)
- In the case of death, the cause and post-mortem findings (if available).

The assessor will fill out a 'Narrative Second Assessment Form' for each SAE containing at least the following information:

- i) Assessment of relationship between SAE and IMP;
- ii) Assessment of expectedness of SAE (derived from SmPC);
- iii) Assessment of relationship between SAE and underlying disease
- iv) Statement if the benefit/ risk assessment for the trial did change as a result of the SAE.

The expedited reporting (to IRB / EC and investigators) will be carried out by the responsible Safety Officer.

The expedited reporting will be carried out after unblinding. Only SUSARs/SAEs occurring after administration of the IMP will undergo expedited reporting. In case of a SUSAR after

EudraCT: 2021-001633-40	Version 1.7 15.01.2025	ESRA
-------------------------	---------------------------	------

administration of placebo a decision regarding the need of expedited reporting will be taken after deliberation between the assessor and the Principal Investigator.

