7.7 Randomization and blinding

After the pre-treatment phase, eligible subjects will be randomized at Visit 1 in a 1:1 ratio to the following 2 treatment groups:

- Riociguat (MK-4836) 1.0-2.5 mg group (titration between 1.0 mg and 2.5 mg tid based on an individual dose titration scheme) (35 subjects planned)
- Placebo group (placebo tid) (35 subjects planned)

Investigator, sponsor, study personnel, monitor, biometrician, and the patient will be blinded to treatment. The sponsor will engage an independent qualified external service (e.g. pharmacy) to

EudraCT: 2021-001633-40	Version 1.7 15.01.2025	ESRA
-------------------------	---------------------------	------

centrally generate the randomization envelopes and emergency envelopes for each participating center.

Earlier screening failures may be rescreened once for possible study entry. Patients who dropped out of the study are not allowed to re-enter or to be enrolled again.

Randomization to one of the groups will be performed by permuted block randomization. Blocks will be stratified according to centre. Randomization lists will be created by the above-mentioned unblinded independent, central external service designated by the sponsor. The randomization list will be kept centrally in safe and confidential custody at the external service in compliance with applicable local laws/regulations.

Emergency Envelopes: In addition to the trial medication the investigator will receive a set of sealed envelopes, one for each randomization number. These envelopes will be created by the unblinded independent, central external service (e.g. pharmacy) in charge of randomization and provided according to the random number with the study medication. An identical set of sealed envelopes will be held at Pharmacovigilance Safety Officer. These envelopes contain information on the subject's trial medication and are to be opened only under circumstances in which it is medically imperative to know what the subject is receiving. Date and reason for opening a sealed envelope must be documented. If possible, the investigator will confer with the Coordinating Investigator before unblinding. The randomization envelopes are not to be opened by the investigator at the end of the trial. All envelopes will be collected by the monitor at the end of the trial.

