9.1.4 Suspected Unexpected Serious Adverse Reaction (SUSAR)

SAEs that are both suspected, i.e. possibly related to IMP and ‘unexpected’, i.e. the nature and/ or severity of which is not consistent with the applicable product information are to be classified as Suspected Unexpected Serious Adverse Reactions (SUSARs). The definition covers also medication errors and uses outside what is foreseen in the protocol, including misuse and abuse of the product.

In case, either the investigator who primarily reported the SAE or the second assessor classify the SAE as ‘suspected’ (i.e. either *related* or *probably* or *possibly related* to the IMP or *not assessable*) and the SAE is unexpected it will be categorized as a SUSAR.

EudraCT: 2021-001633-40	Version 1.7 15.01.2025	ESRA
-------------------------	---------------------------	------

All SUSARs are subject to an expedited reporting to the responsible IRB / EC and to all participating investigators.

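### The expedited-reporting rule in Protocol 9.4 reveals placebo allocation to the Principal Investigator and gives sites no blinded report, contrary to the blind in 7.7

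*Protocol*

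**What the plan says.** **The blind.** Protocol 7.7 names who is kept unaware: "Investigator, sponsor, study personnel, monitor, biometrician, and the patient will be blinded to treatment". The emergency envelopes "are to be opened only under circumstances in which it is medically imperative to know what the subject is receiving". Section 9.5 gives the same single ground. A duplicate set exists: "An identical set of sealed envelopes will be held at Pharmacovigilance Safety Officer". SAP 1.3 repeats that patients and investigators were blinded. None of these places lists SUSAR reporting as an exception.

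**The reporting rule.** Under Protocol 9.4, SUSARs are to be "reported to all involved investigators and competent IRB / EC", within 15 days, or within 7 days if fatal or life-threatening. Further on: "The expedited reporting (to IRB / EC and investigators) will be carried out by the responsible Safety Officer". The next statement is "The expedited reporting will be carried out after unblinding". The section then limits expedited reporting to events after the IMP and treats placebo separately. For a SUSAR after "administration of placebo a decision regarding the need of expedited reporting will be taken after deliberation between the assessor and the Principal Investigator".

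**The competing rule.** Section 9.1.4 makes no distinction by arm: "All SUSARs are subject to an expedited reporting to the responsible IRB / EC and to all participating investigators".

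**The concern.** Section 9.4 requires something that 7.7 and 9.5 do not allow. A SUSAR must be serious, suspected and unexpected, but it need not make knowledge of the treatment a medical necessity. The code is nevertheless opened, and nothing says that the allocation stops with the Safety Officer.

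The people who might learn it make judgements that feed the results. Investigators judge AE causality (9.1.6), adjust the dose (8.3.3) and may start rescue medication at their discretion (6.7). WHO functional class and 6-minute walking distance are assessed at site and are both in the hierarchical secondary list (10.3.1). Section 12.8 writes the coordinating and principal investigator roles as one, and 6.5.1 gives the Coordinating Investigator the decision on withdrawal from treatment. Randomisation is in permuted blocks within centre (7.7), so an allocation known at a site could also help in guessing others in the same block there. The block size is not stated, so that effect cannot be sized.

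**Working it through.** The plan states no figure on this point, so the check is mainly a comparison of texts.

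**Step 1. Does the placebo discussion reveal the arm?** Under 9.4 the discussion with the Principal Investigator arises only when the case is known to be on placebo. Being consulted is therefore enough to learn the arm. The synopsis places the Principal Investigator at Heidelberg. The centre table in SAP section 3 gives Heidelberg 23 of 35 patients: 23/35 = 65.7%. This disclosure follows from the text without further assumption.

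**Step 2. Are other investigators protected?** Reports to them follow unblinding. No section provides a blinded copy, and none says that the copy states the arm. The documents leave this open.

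**Step 3. Could a site infer the arm from whether a report appears?** Assume 1:1 allocation, every riociguat SUSAR reported, and a share q of placebo SUSARs reported. Let r be the ratio of SUSAR rates, riociguat to placebo. Neither q nor r is in the documents; both are assumptions. Then

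- P(riociguat | SUSAR) = r/(r + 1) before anything is known about reporting;
- P(riociguat | SUSAR reported) = r/(r + q);
- P(placebo | SUSAR not reported) = 1 for any q below 1.

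| r | before reporting | q = 0 | q = 0.25 | q = 0.5 | q = 1 |
|---|---|---|---|---|---|
| 0.5 | 33% | 100% | 67% | 50% | 33% |
| 1 | 50% | 100% | 80% | 67% | 50% |
| 2 | 67% | 100% | 89% | 80% | 67% |

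For example, r = 1 and q = 0.5 gives 1/(1 + 0.5) = 67%. Only at q = 1 does the report add nothing to the starting probability, and 9.4 does not require q = 1. The last formula holds for an event known to be a SUSAR. Under 9.4 expectedness is assessed on the second assessor's form, so a site that sees no report may also wonder whether the event was judged expected. The inference is then weaker than certainty.

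**Step 4. Do 9.1.4 and 9.4 agree?** Section 9.1.4 amounts to q = 1. Section 9.4 leaves q to case-by-case decision. Both cannot be followed. The synopsis also labels placebo as an IMP, which blurs the limit to events after the IMP, although the following sentence of 9.4 clearly sets placebo apart.

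**Step 5. Which outcomes are exposed?** Under 8.2.2 the catheter recordings are also read centrally by two physicians blinded to treatment, and SAP 1.3 keeps the statistician blinded during analysis. This protects PVR in part. The protection is not complete, because the centres also enter their own measurements and neither document says which reading supplies the analysed value. Functional class, walking distance, causality, titration and rescue have no such second reading.

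**The case against.** The other side has a good case on scope.

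- **Content of the reports.** Unblinding before reporting describes an order of steps by the Safety Officer, not what the report says. A reader might infer that every SUSAR discloses an allocation at all eight planned sites. The documents do not support that: no section says investigators' copies state the arm, placebo cases may not be reported at all, and two centres (Dresden and Naples) enrolled nobody. A report reaching another centre cannot bias the rating of that patient, and does not help with blocks that are stratified by centre. The exposure that matters is at the patient's own site.
- **Routing.** If 9.1.4 governs, routing reveals nothing. This is correct, but it rests on one of two conflicting rules.
- **Pseudonymised reports.** Section 9.4 requires this, and it helps for patients elsewhere. It helps little where the Principal Investigator's own centre reported the case.
- **Frequency.** A reader might want to put a percentage on the patients disclosed. No SUSAR count is given. The drug is already approved and expectedness is judged against its product information, so zero among 35 patients is plausible. Any assumed count would be a guess. Some patients with a SUSAR may also have stopped treatment under 6.5.1.
- **Timing.** Enrolment ended at 35 and the trial was terminated early, so new wording cannot restore a blind already lost. This stands for the protocol text, but not for disclosure in the analysis.
- **Safety Officer.** Unblinding by the Safety Officer alone would not reach site staff and is not the fault. The fault is the missing barrier after that step.

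None of this removes the Principal Investigator's exposure, the missing provision for blinded reports, or the conflict between 9.1.4 and 9.4.

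**Conclusion.** The point holds, within limits, and should be corrected. The Principal Investigator's learning of placebo status is explicit in 9.4. Inference by the patient's own site depends on placebo SUSARs sometimes going unreported and on the site recognising the event as a SUSAR. The conflict between 9.1.4 and 9.4 is independent of both.

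The effect is confined to patients who have a SUSAR, apart from any guessing within blocks at the same site. Each such patient would be 1/35 = 2.9% of those enrolled; how many there were, if any, the documents do not say. A reader might infer that the PVR comparison is biased. The documents do not support that conclusion, given the blinded central reading and the unknown count, and the size of any bias cannot be calculated from them.

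**What to change.** - In Protocol 9.4, confine unblinding for expedited reporting to the Safety Officer and the report to the IRB/EC.
- Send all investigators, including the Principal Investigator, the same blinded report whichever arm the case came from.
- Have the Safety Officer, or an assessor outside trial conduct, take any decision on placebo SUSARs.
- Align 7.7, 9.1.4 and 9.4: add the reporting exception to 7.7, and state one rule on whether placebo SUSARs are reported.
- Because the trial has already ended early, add to the SAP a listing of any patients whose allocation reached site staff or the Principal Investigator through SUSAR reporting. If there were none, say so.

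The cost is protocol and SAP wording plus a blinded version of each report. No new code holder is needed, because the Safety Officer already has the duplicate envelopes. Investigators can still learn the arm in an emergency under 9.5.

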9.5 Emergency Unblinding

If it is medically imperative to know which trial medication the subject has received, the investigator or authorized person should open the emergency envelope. The investigator or the person who breaks the blind must record the date and the reasons for doing so in the CRF, in the subject's medical record, and on the emergency envelope. Whenever possible, the Coordinating Investigator should be contacted before the blind is broken.

9.6 Emergency Treatment

During and following a subject's participation in the trial, the investigator should ensure that adequate medical care is provided to a subject for any AE including clinically significant laboratory values. The investigator should inform a subject when medical care is needed for intercurrent illness(es) of which the investigator becomes aware.

In case of clinical worsening and if clinically indicated additional PAH-targeted rescue medication will be initiated.

10 Statistical Procedures

10.1 Sample Size Calculation

In this randomized study patients with early pulmonary vascular disease, indicated by either a) mPAP ≥ 25 mmHg with PVR ≥ 2 to < 3 WU and PAWP ≤ 15 mmHg or b) mPAP 21- < 25 mmHg with PVR ≥ 2 WU and PAWP ≤ 15 mmHg will be randomized into two groups: one group receiving riociguat (MK-4836) and one placebo group.

In the EDITA study (Pan et al. 2019) SSc patients with mildly elevated mPAP 21-24 mmHg showed a significant reduction of PVR after 6 months of treatment (control-group 0.02 ± 0.76 vs. intervention group -0.59 ± 0.79 WU; effect size 0.77). The changes in PVR were equal to a $23.87 \pm 35.68\%$ reduction in the intervention group and increase by $5.44 \pm 36.61\%$ in the control group (effect size 0.81).

A meta-analysis showed an effect size of 0.88 in both PAH and CTEPH (Zhao et al. 2019).

In the retrospective analysis of patients with CTD-APAH receiving riociguat in PATENT-1 and PATENT-2, mean improvement of PVR after 12 weeks was 132 ± 140 dynes*sec*cm $^{-5}$ in patients with SSc (equals 1.65 ± 1.75 WU; effect size 0.94; Humbert et al. 2017). Patients with SSc-PAH had an effect size of 0.97 (Humbert et al. 2017).

EudraCT: 2021-001633-40	Version 1.7 15.01.2025	ESRA
-------------------------	---------------------------	------

In this study, patients with PVR \geq 2WU will be included. The use of the effect size of the EDITA study for sample size calculation leads most likely to an underestimation of the effect, as in this study with ambrisentan most patients showed a PVR <2 WU at baseline. Furthermore, all studies reported in the table below had a study duration of 12 weeks. A study duration of 24 weeks will lead to a higher effect and reduction of PVR. Therefore, we assume an effect size of 0.87 of riociguat (MK-4836) treatment in this study. A comparable effect size for both included subgroups is anticipated for this study.

Reference	Change / difference in PVR	Effect size	Power	Sample size without dropout
Pan 2019; EDITA	SSc: 0.61 \pm 0.79 WU (Ambrisentan)	0.77	80%	56
Pan 2019; EDITA	SSc: -23.87 \pm 35.68% (n=17) in the intervention group and increase by 5.44 \pm 36.61% (n=15) in the control (Ambrisentan)	0.81	90%	66
Zhao 2019 Meta-analysis Riociguat	PH (PAH and CTEPH): n=695 (Riociguat)	0.88	85%	50
Humbert 2017 CTD-APAH from PATENT-1 and 2	SSc: 1.65 \pm 1.75 WU Other CTD: 3.45 \pm 3.54 WU (Riociguat)	0.94 0.97	90% 90%	50 48
A sample size of 58 will lead to n=70 with dropout of 15%.				

If the true treatment effect is at least a 30% reduction of PVR (effect size is 0.87), a sample size of 29 patients/group (total 58 patients) achieves a statistical power of 90.2% to reject the null hypothesis, according to the two-sample student's t-test, with a type I error of 0.05 (two-sided). With the sample size of 70 patients and a dropout of 15% (valid sample size n=58), we achieve a 90.2% power, if the means of PVR differ by at least 30% and both groups have an equal standard deviation of 34.5%. A sample of 70 patients (35 patients in each group), allocated in a 1:1 ratio, will therefore be included.

The primary endpoint will be analyzed by an analysis of covariance (ANCOVA) with baseline values as covariates, which has a power advantage over the student's t-test, achieving a statistical power of 90.2% or more. If the preconditions for ANCOVA are not met, a student's t-test assuming unequal variances (Welch-test) will be performed.

EudraCT: 2021-001633-40	Version 1.7 15.01.2025	ESRA
-------------------------	---------------------------	------

10.2 Definition of Trial Population to be analyzed

All patients randomized and treated will be valid for the modified intention-to-treat population, hence the numbers of patients in the safety and modified intention-to-treat populations will be identical. In the modified intention-to-treat analysis set, patients will be analyzed according to the group allocation they were randomized into. The primary endpoint will be analyzed in a complete case analysis.

As patients with only mild changes of hemodynamics will be included in this study, it is not assumed that the severity of pulmonary vascular disease will affect the participation in the follow-up examination. A complete case analysis is considered as valid, as participation of the follow-up examination is assumed to be completely at random.

As sensitivity analysis, multiple imputation for the primary endpoint will be performed and analyzed.

A randomized patient is valid for safety / modified intention-to-treat analysis, if at least one dose of study medication was administered.

A patient is valid for the per protocol analysis, if the patient is valid for the safety / modified intention-to-treat analysis, has an adequate PVR investigation at baseline and at week 24 or if withdrawn due to lack of efficacy has an adequate PVR investigation at any time post-baseline up to week 24, and shows no major protocol deviations.

Major protocol deviations are:

1. Patients who do not meet the inclusion criteria
2. Administration of IMP not according to protocol (e.g. compliance less than 80% or greater than 120% (corresponding to an overdose))

The above specifications of the analysis populations are in accordance with the recommendations given in the ICH-E9 Guideline “Note for guidance on statistical principles for clinical trials”.

EudraCT: 2021-001633-40	Version 1.7 15.01.2025	ESRA
-------------------------	---------------------------	------

10.3 Statistical Methods

10.3.1 General

Descriptive statistics

All variables will be analyzed descriptively with appropriate statistical methods: data (demographic and other baseline characteristics, continuous data at each visit and their change to baseline) will be listed and trial summary tables will be provided.

Descriptive statistics will be displayed by treatment, including the usual location and scale statistics (mean, median, standard deviation, standard error, first and third quartiles, minimum and maximum) and 95% confidence limits of mean and median.

Frequency tables for qualitative data will be provided.

Demographic variables and baseline characteristics will be summarized by treatment group for both analysis populations (i.e. valid for safety / modified intent to treat analysis (ITT), valid for per protocol analysis). Wherever possible (i.e. sufficient sample size), centres will be considered for the analyses.

Hypotheses and statistical inference

Null-Hypothesis (H_0):

The means of the changes of the primary endpoint from baseline to follow-up after 24 weeks in the treatment and control group are the same.

Alternative hypothesis (H_1):

The mean change of the primary endpoint from baseline to follow-up after 24 weeks in the treatment group differs from the mean change in the control group.

Type I error

If not mentioned otherwise, all statistical tests will be performed with a type I two-sided error rate of $\alpha=0.05$

Efficacy analysis

The primary efficacy analysis will be performed in patients valid for modified intention-to-treat analysis. The per-protocol analysis will be supportive.

EudraCT: 2021-001633-40	Version 1.7 15.01.2025	ESRA
-------------------------	---------------------------	------

Primary endpoint

The evaluation of the primary efficacy endpoint will be the change from baseline to 24 weeks in pulmonary vascular resistance. The primary analysis set will be a complete case analysis of the modified intention to treat set.

The main comparison will be the difference in treatment effect between riociguat (MK-4836) and placebo. 95% confidence intervals of treatment difference will also be calculated. The primary comparison will be an ANCOVA model including baseline scores as covariate.

If the preconditions for an ANCOVA analysis are not met, the primary endpoint will be analyzed by robust, two-sided t-test (Welch-test).

Secondary efficacy variables

All secondary analyses will be exploratory and will be considered descriptively. Secondary parameters at baseline and during follow-up will be compared between groups comparing the difference between baseline and follow-up visits. Data will be displayed by means and standard deviations, medians and variances with respective 95% confidence intervals. p-values <0.05 will be considered as statistically significant.

Secondary endpoints will be statistically analyzed by a hierarchical testing strategy using the two-sided student's t-test with comparison of the differences between riociguat (MK-4836) and placebo.

The sequential testing procedure will be performed for these six secondary efficacy variables, strictly in the order listed

- change of cardiac index at rest (baseline to 24 weeks)
- change of total pulmonary resistance (baseline to 24 weeks)
- change of diffusion capacity of the lung (baseline to 24 weeks)
- change of 6-minute walking distance (baseline to 24 weeks)
- change of WHO functional class (baseline to 24 weeks)
- change in QoL (SF-36, physical summation score; baseline to 24 weeks)

It is assumed that WHO functional class will either remain the same, improve by one or two categories, or deteriorate by one category in most cases. A change score (baseline minus end of study) will be calculated, which could go from -3 (class IV at baseline and class I at end of study) to +4 (class I at baseline, death at end of study), but in practice for those patients still alive at the end of the study it will most likely range from -2 to +1.

EudraCT: 2021-001633-40	Version 1.7 15.01.2025	ESRA
-------------------------	---------------------------	------

Exploratory endpoints

Further outcome parameters will be tested exploratory and reported with 95% confidence intervals of the difference between changes in the intervention and placebo group, mean and standard deviation of the mean. Parameters will be analyzed as change from baseline to 24 weeks riociguat (MK-4836) vs. placebo; if available as per visit and assessment schedule, changes between baseline and 12 weeks will also be analyzed.

Patients who withdraw from the study will be asked to complete a final examination which will be included in the data analysis.

Parameters for explorative data analysis include

WHO functional class (baseline to 12 weeks)

Echocardiography

- sPAP, RV-area and RA-area, TAPSE, LV-EI, RV-pump function and LV-EF.

QoL assessed by the short form of the medical outcome questionnaire (SF-36 questionnaire)

- (mental summation score as well as the 8 sub-scores)

Lung function and lung diffusing capacity

- FEV1 (forced expiratory volume in 1 second), TLC (total lung capacity), DLCO (diffusing capacity of the lung)

Blood for blood gas analyses:

- oxygen partial pressure, carbon dioxide partial pressure, SpO₂, pH values, bicarbonates, base excess

Analyses of blood samples:

- NT-pro BNP

Pulmonary hemodynamics by right heart catheterization:

- CI, sPAP, mPAP, dPAP, PAWP, RAP, PVR, CO, SvO₂

EudraCT: 2021-001633-40	Version 1.7 15.01.2025	ESRA
-------------------------	---------------------------	------

Sensitivity analyses

Sensitivity analyses will be performed to investigate the effect on patients with higher vs. lower PVR and higher vs. lower mPAP. A multiple imputation strategy will be implied and analyzed for the primary endpoint.

Safety analysis

The safety analysis will be performed in the population valid for safety. All tabulations will be descriptive only. Tables will be produced for drug-related treatment-emergent adverse events and serious adverse events. Further tables will be produced for serious and/or drug-related treatment-emergent adverse events.

Mortality in the 24-week period of the study will be summarized descriptively. Any deaths in the study period will be listed, with day of death relative to start and stop of study drug and cause of death.

The safety evaluation of laboratory data will include:

listings of laboratory data out of normal range, evaluation of the significance if they are out of normal range, descriptive analysis of continuous laboratory parameters and their changes from baseline by visit and treatment group. Vital signs will be summarized by visit and treatment group.

Clinical worsening (as exploratory safety endpoint) will comprise of the following parameters:

- worsening of WHO functional class
- deterioration of 6MWD >15% compared to baseline
- need of initiation of targeted PAH treatment
- hospitalization due to worsening of right heart function
- all cause death or lung-transplantation
- atrial septostomy

Biometric analysis will be defined in the statistical analysis plan which has to be authorized before data base lock by the biometrician and the Coordinating Investigator.

EudraCT: 2021-001633-40	Version 1.7 15.01.2025	ESRA
-------------------------	---------------------------	------

11 Data Management

